3.6.1. Informed consent and enrolling

Volunteers Will be recruited at High complexity Health institutions that are part of the study. Through direct invitation either personal or by email. An information sheet for the participant Will be done (appendix 5. According to good clinical practice and considering eligibility criteria one of the investigators will perform the informed consent process explaining study objectives, potential benefit, and risks. After verifying understanding by the potential participant, the informed consent format will be signed according to current regulation.

3.6.2. Baseline evaluation

The doctor assigned to the study takes a medical history that includes a review of systems, past medical history, and a complete physical examination. In addition, he or she will order laboratory exams described in Table 1. In case of clinical or laboratory alteration defined in the exclusion criteria, the volunteer will be excluded and will not continue in the following phases. Additionally, a RT-PCR will be carried out with a nasopharyngeal swab sample and a serological test of IgG antibody titers against SARS-CoV-2. In case of having any of the previously mentioned tests positive, the volunteer will be excluded. Female volunteers will undergo qualitative β -HCG and, if positive, they will be excluded or if they report the desire to become pregnant in the next two months. At 24 to 48 hours with the results of the examinations and a new anamnesis the eligibility of the volunteer will be confirmed. If so, the randomization process will be carried out and the intervention will be delivered according to the process defined in the concealment section of allocation (3.6.4) and administration of the intervention product or placebo (3.6.5).

3.6.3. Randomization

A simple randomization will be carried out, considering that it is not deemed necessary to stratify by any characteristics of the individuals, or by center. Additionally, due to the size of the sample there is little possibility of presenting a significant imbalance between the groups regarding characteristics that affect the outcome.

The randomization will be carried out with a 1:1 relationship between the active intervention and the placebo, a randomization system generated by the REDCap software will be used, with random numbers that will meet the following requirements: each volunteer will have a known probability, and equal to be assigned to any of the interventions, future assignments will not be predictable based on previous assignments, the order of assignment will be reproducible.

The randomization will be carried out centrally, by a trained member of the HUSI research office, who is not part of the research group, or the study staff, after generating the randomization, this will be communicated exclusively to the central pharmacist of the research team.

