3.4. Sample size

An estimative of the number of required participants was done according to the following parameters:

- Risk of SARS-CoV-2 infection reported in the world: despite of the little data available on incidence reports from China, The Netherlands and Madrid vary from 6 to 38.9 per 100 exposed health care workers. The high variability on the incidence is related to the develop of institutional outbreaks, thus establishing a latent risk in all hospital institutions in a pandemic scenario (7,44,76). To assess the sampling size calculation for this study, besides what has been reported internationally, an approximate calculation of the incidence of SARS-CoV-2 infection in the health care institutions in which the study will be held was performed. It is important to know the infection and epidemic control variates from one institution to another. While some actively screen asymptomatic health care personnel others only screen symptomatic health care personnel. The incidence observed in a 2-month period of time variates between 3.3% and 13.7% with a mean of 11.2 cases per 100 health care workers.

Based on that preliminary information, an expected risk for SARS-CoV-2 infection in the control group (Placebo + PPE) of 0.10 was used for the calculation. With the objective of estimating precisely a 50% relative risk reduction an assumption of an expected risk of 0.05 was done in the intervention group (Tenofovir/Emtricitabine + PPE) in order for a difference of 0.05 to detect between both groups.

- Power: 0,80. Alfa level: 0.05
- Assigantion ratio $n_1/n_2 = 1:1$ (randomization1: 1).
- Sample size: 858 (429 per group).

Considering possible loses up to 10% it is risen to 950 in total (with randomization 475 participants to each group).

As a limitation of the study, if the incidence or the effect of the interventions are considerably lower than expected, the power to detect significant differences between both groups will be reduce. However, due to the progression of the pandemic in our country, with a tendency to increase, it is probable that the incidence observed in health care professionals will remain stable or even increase not only for the intrahospital risk, but for the risk in the community,

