3.6.4. Allocation concealment

Mechanisms will be applied to ensure concealment of randomization. The decision to include a volunteer in the study will be made without knowing the intervention that said individual will receive if they participate, that is, neither the investigators nor the study personnel will know the assignment before the start of the intervention. The following strategies will be used in the study to ensure this:

- The randomization will be carried out centrally, the center that sends the volunteer to randomize at the central level, ensures that he meets all the eligibility criteria and registers the volunteer in the REDCap system, in such a way that it is impossible to subsequently change the allocation generated.
- Prior to the start of recruitment, the central pharmaceutical chemist will mark 1000 bottles with labels with randomly assigned numerical codes, to the 500 bottles corresponding to TDF/FTC 300/200mg and the other 500 bottles containing placebo. The only one who will know the information on the specific contents of the vials is the central pharmaceutical chemist of the study.
- The person who will carry out the randomization process is not part of the research group or the research team, he will receive a notification by telephone and by REDCap, that there is a volunteer who is eligible to participate in the study. Through REDCap the random assignment will be generated, and the system will give you the code of the bottle that the volunteer should receive. This person will only inform the central pharmaceutical chemist, the code of the bottle that the subject must receive.
- The central pharmaceutical chemist will communicate with the local pharmaceutical chemist, by means of a telephone call, and will inform him of the code of the bottle that must be given to each volunteer. The local pharmaceutical chemist will be blind to the intervention.
- In REDCap a record will be kept of the selection of the study patient, as well as the fulfillment of the delivery of the bottle assigned by the program.

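### Simple unstratified randomisation does not guarantee 475 per arm: with 500 bottles per arm and no stock-out rule, one arm runs out in about 10% of trials, and balance within sites is left to chance

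*Combined protocol and SAP*

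**What the plan says.** **Allocation.** Section 3.6.3: "A simple randomization will be carried out, considering that it is not deemed necessary to stratify", whether on individual characteristics or on centre. The ratio is equal: "The randomization will be carried out with a 1:1 relationship between the active intervention and the placebo". It also requires that "each volunteer will have a known probability, and equal to be assigned to any of the interventions" and that no assignment can be predicted from those before it. No blocking is described. The reason given is that a sample of this size makes an important imbalance in characteristics unlikely; arm sizes and drug supply are not discussed.

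**Numbers.** Section 3.4 raises 858 to 950 for losses, "with randomization 475 participants to each group".

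**Supply.** Section 3.6.4 has 1000 bottles labelled before recruitment, with codes given "to the 500 bottles corresponding to TDF/FTC 300/200mg and the other 500 bottles containing placebo". Section 3.6.5 hands each volunteer all 60 tablets at the start. Section 9.2 buys 30,000 tablets of each product, although its justification is 475 volunteers for 60 days.

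**Release of bottles.** REDCap generates the assignment and returns a bottle code. Then "The central pharmaceutical chemist will communicate with the local pharmaceutical chemist" by telephone to pass the code on. How stock is divided among hospitals is not stated.

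**Sites and analysis.** Section 3.4 says of the participating institutions: "The incidence observed in a 2-month period of time variates between 3.3% and 13.7" per cent, and notes that some screen asymptomatic staff and others do not. Section 3.2 says seven institutions but names eight, and Appendix 3 codes eight. Section 4 plans a univariate Cox model, with adjustment only if variables turn out unbalanced.

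**The concern.** Three statements have to work together: independent 1:1 assignment, 475 per arm, and a fixed stock of 500 bottles per arm. Under independent assignment the arm sizes vary by chance, and nothing in the plan holds them under 500. If one arm's bottles run out, the next volunteers assigned to that arm must either wait or be given the other product. In the second case their allocation is no longer random. The plan gives the central pharmacist, the one person in the chain who knows the contents of the bottles, no rule to follow.

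A second issue does not depend on supply. Infection incidence differs between the hospitals by the plan's own account, yet neither the randomisation nor the primary model takes account of site. The adjustment rule in Section 4 does not fill the gap: its triggers are an odds ratio for dichotomous variables and a standardised difference for continuous ones, and an eight-category site variable fits neither.

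**Working it through.** **1. The plan's sample size.** Inputs from Section 3.4: risks 0.10 and 0.05, power 0.80, alpha 0.05 (taken as two-sided; the plan does not say).

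- Unpooled formula: (1.960 + 0.842)² × (0.10×0.90 + 0.05×0.95) / 0.05² = 432 per arm. The pooled formula gives 435 and the arcsine formula 424. The stated 429 lies within this range.
- Losses: 858 / 0.9 = 954 and 858 × 1.1 = 944. The stated 950 lies between them.

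The planned size is therefore not in dispute.

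**2. Arm size under simple randomisation.** Let X be the number assigned to one arm, X ~ Binomial(950, 0.5).

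- Mean 475; SD = √(950 × 0.25) = 15.4.
- 95% range: 445 to 505.
- P(exactly 475/475) = 2.6%.

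**3. Supply.** 30,000 tablets / 60 = 500 bottles per arm, which agrees with Section 3.6.4. Margin: 500 − 475 = 25 bottles, and 25 / 15.4 = 1.6 SD.

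**4. Chance that one arm runs out.** Both arms cannot exceed 500 when 950 are randomised, so the two tail probabilities add:

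- P(X > 500) = 0.0490; doubled, 0.098.
- Simulation gives the same 9.8%.
- If 944 are randomised the figure is 6.4%; if 954, it is 12.8%.
- Given a run-out, the mean number of assignments beyond the 500th bottle is 6.9, or about 0.7 averaged over all trials (0.098 × 6.9).

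**5. The other reading: codes drawn without replacement from the list of 1000.** No arm can exceed 500. SD = √(950 × 0.25 × 50/999) = 3.4, and the 95% range is 468 to 482. Each assignment probability now depends on the assignments already made, so this is not simple randomisation.

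**6. Balance within a site.** As an assumption, recruitment equal across eight sites gives 950 / 8 ≈ 119 per site. One arm at such a site has SD √(119 × 0.25) = 5.5. The chance of a split more extreme than 60:40 is 2.7% with 119 participants, 9.2% with 60 and 20% with 30. The smaller sites are the exposed ones.

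**7. Power.** At 475/475 it is 83.4%. At 450/500 it is 83.1% to 83.5%, depending on which arm is larger.

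**8. Permuted blocks of 4 and 6 within eight sites.** At any moment a site's open block can be out of balance by at most 3. The total difference between arms is at most 8 × 3 = 24, so the larger arm is at most (950 + 24) / 2 = 487, below 500.

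**9. Simple randomisation with more stock.** With 515 bottles per arm, P(either arm exceeds 515) = 0.9%.

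**The case against.** The strongest reply is that this is a small operational matter in a valid design. Simple randomisation of 950 people is unbiased. The figure of 475 is a planning value already raised from 429 for losses, and the chance that either arm falls below 429 is only 0.25%. Enrolling staff and local pharmacists are blind, so they could not exploit a forced late assignment. A volunteer who waits for resupply keeps a random allocation. All of this stands, and it is why the point is minor.

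It can also be said that REDCap may simply draw from the 1000 codes, in which case no arm can run out. That is a possible reading of Section 3.6.4, but it conflicts with the simple randomisation in Section 3.6.3. The text needs correcting either way.

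A reader might infer more than the documents support:

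- *That there is no reserve.* There is one: 25 bottles per arm, or 5.3% of 475. It is modest against the chance variation, but it exists.
- *That individual sites will almost surely run out.* This needs an even split of stock, one shipment and no transfers. The documents say nothing on how stock is divided, so no site-level run-out figure is given here.
- *That true risk differs four-fold between sites.* The 3.3% to 13.7% range partly reflects who was screened, whereas the trial tests everyone on one schedule. Nor does the plan rank site against other risk factors.

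**Conclusion.** The point holds as a minor one. As written, the plan does not guarantee 475 per arm, and there is about a 9.8% chance that one arm exhausts its 500 bottles, with about 7 allocations then forced or delayed. This assumes exactly 950 randomised, independent assignment, one bottle each, no breakage or replacement, and no resupply. If the fixed code list is used instead, the run-out risk is zero, but the stated method is then wrong and balance within sites remains uncontrolled.

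It would be wrong to conclude that the trial cannot reach its planned size or that its power is at risk: the change in power is below half a percentage point. What is at stake is the integrity of the last few allocations and the handling of site. Incidence differs between institutions to an extent the documents do not let us separate from screening practice, and the univariate primary model ignores it.

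**What to change.** **Preferred.** Replace simple randomisation with permuted blocks of randomly varying size (for example 4 and 6), stratified by centre, in the same central masked REDCap system and with block sizes not disclosed to sites. The larger arm then stays at or below 487 and the existing 500 bottles suffice. Stratify the primary Cox model by site, which Appendix 3 already records. Correct the number of institutions in Section 3.2 so that the strata are defined.

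**If simple randomisation is kept.** Hold about 515 bottles per arm (run-out risk about 0.9%), write down what happens to a volunteer whose assigned arm is out of stock, state how REDCap links assignments to bottle codes, and still stratify the Cox model by site.

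**Cost.** The preferred change needs a new allocation table before recruitment and a sentence or two in Sections 3.6.3 and 4. Blocks make assignments slightly less unpredictable in principle, which is negligible when allocation is central and masked. The alternative costs about 15 extra bottles per arm, or 15 × 60 = 900 tablets of each product, and leaves balance within sites to chance.

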3.6.4. Allocation concealment

Mechanisms will be applied to ensure concealment of randomization. The decision to include a volunteer in the study will be made without knowing the intervention that said individual will receive if they participate, that is, neither the investigators nor the study personnel will know the assignment before the start of the intervention. The following strategies will be used in the study to ensure this:

- The randomization will be carried out centrally, the center that sends the volunteer to randomize at the central level, ensures that he meets all the eligibility criteria and registers the volunteer in the REDCap system, in such a way that it is impossible to subsequently change the allocation generated.
- Prior to the start of recruitment, the central pharmaceutical chemist will mark 1000 bottles with labels with randomly assigned numerical codes, to the 500 bottles corresponding to TDF/FTC 300/200mg and the other 500 bottles containing placebo. The only one who will know the information on the specific contents of the vials is the central pharmaceutical chemist of the study.
- The person who will carry out the randomization process is not part of the research group or the research team, he will receive a notification by telephone and by REDCap, that there is a volunteer who is eligible to participate in the study. Through REDCap the random assignment will be generated, and the system will give you the code of the bottle that the volunteer should receive. This person will only inform the central pharmaceutical chemist, the code of the bottle that the subject must receive.
- The central pharmaceutical chemist will communicate with the local pharmaceutical chemist, by means of a telephone call, and will inform him of the code of the bottle that must be given to each volunteer. The local pharmaceutical chemist will be blind to the intervention.
- In REDCap a record will be kept of the selection of the study patient, as well as the fulfillment of the delivery of the bottle assigned by the program.

3.6.5. Administration of the intervention product and placebo

Volunteers assigned to the intervention group will receive one tablet of TDF/FTC 300/200mg each day. Each volunteer will be given 60 tablets of the medicine at the beginning of the treatment and its administration will be verified daily by sending a virtual survey, in which the subject answers if he took the intervention, plus a follow-up diary that will be given to the patient of Virtual or manual way for people without access, to write adverse events, as well as the hours of daily exposure to patients with suspected or diagnosed COVID 19 and adherence to personal protection elements. These data will be stored in an eCRF for clinical follow-up, adverse events, and adherence.

Patients assigned to the control group will receive a placebo that will have the same appearance and size and will not have any active ingredients. Similarly, 60 placebos will be delivered from the start of treatment.

The medicine must be stored at a temperature not exceeding 30 ° C and in an environment without excessive humidity in its authorized container and packaging.

3.6.6. Blind or masked evaluation

To control for biases related to the measurement or evaluation of the study subjects, during the study, it will be ensured that the investigators and the volunteers are blind to the assigned intervention.

To ensure that the volunteer is blind to the intervention, they will not be informed which intervention they are receiving (tenofovir / emtricitabine or placebo) and additionally a placebo with a taste and presentation similar to tenofovir / emtricitabine will be used, on the other hand, the vials in which both the active drug and the placebo will be packed, they will be the same and will only be differentiated by the numbers on the labels.

The researcher will be blind throughout the volunteer's follow-up, and this will be ensured because a central randomization will be carried out, only the central pharmaceutical chemist will know the assignment and the researcher will only know the code of the drug that the patient receives, which is not decodable.

Finally, the person in charge of data analysis will receive a database that will be downloaded from REDCap, in which there will be a code that will identify which of two different interventions a volunteer has received, but which will not allow identifying whether they correspond to tenofovir/emtricitabine or placebo. This coding will only be revealed when the analysis is complete. There is only one person independent of the analysts and the researchers, who knows the code.

3.6.7. Study variables

The study variables are in Annex 3 with their respective conceptual and operational definitions.

3.6.8. Sample processing and interpretation of laboratory tests.

- RT-PCR: it will be processed in the HUSI clinical laboratory for the volunteers of the HUSI, the National University Hospital and the Samaritana Hospitals; The centers of the Colsanitas Group will perform the PCR in the Colsanitas group laboratory and the PCR of the San Jorge Hospital at the

Technological University of Pereira according to the protocols used in each of these institutions, with internal and external quality controls, as well as technical endorsed by the National Institute of Health. The results will be sent within 24 hours after taking the sample to the doctors assigned to the study, who will inform the patient and carry out the pertinent follow-up. (See Annex 6. Diagnostic tests)

- Serological tests for IgG antibodies will be processed in the HUSI clinical laboratory and the Colsanitas Group centers. The qualitative detection of IgG antibodies against SARS-CoV-2 will be carried out in human serum or whole blood obtained from the volunteers, using the immunochromatography test: Standard Q, SD Biosensor®. The antibodies present in the sample form a complex with the antigen labeled with colloidal gold (SARS-CoV-2 recombinant antigen), the complex progresses under the action of chromatography and combines with the coated antibody (mouse monoclonal antibody IgM / IgG anti-human) in the IgG line to form a complex and develop color, which is a positive result. When the sample does not contain the SARS-CoV-2 IgG antibody, the complex cannot form and a red band does not appear on the IgG line, which is a negative result. Regardless of whether either SARS-CoV-2 IgG or IgM antibodies are present in the sample, the gold-labeled quality control antibody will bind to the coated antibody on line C to form a complex and develop color (line C) to validate the test. For the study, only IgG antibody results will be considered, contemplating the high rate of false positives of IgM tests, especially in asymptomatic patients (66).

- Blood samples will be taken by nurses or bacteriologists assigned to the study, who will store, label, and manage them following the SOPs (standard operating procedures) established in each participating center. Complete blood count, liver, kidney function, phosphorus, HIV- ELISA, HBsAg Ab tests will be processed following the SOPs of the clinical laboratories hired for this purpose. The results will be sent via institutional email to the physicians assigned to the study and in charge of monitoring each volunteer. Their interpretation will be carried out in accordance with the values established as normal by said laboratory, in conjunction with the criteria described in this protocol to graduate the severity of AE (See table 4). The results of the paraclinical tests will be interpreted by a doctor assigned to the study who decide on the volunteer's continuity in the study.

3.6.9. Procedure in case of presenting the primary outcome

If the volunteer, after the start of the study, has a positive result of RT-PCR or IgG for SARS CoV2, which confirms the infection by COVID 19, they will be contacted virtually or in person. During this intervention, the following actions will be carried out:

- You will be given information about your result, and you will be instructed to contact your occupational risk and health insurer.
- The presence of alarm signs (drowsiness, dyspnea, cyanosis) will be evaluated. In case of any of these symptoms are present, the patient will be instructed to attend the emergency service, to receive treatment in accordance with current national and institutional guidelines.
- The volunteer will be instructed to suspend the intervention product, and the masking will be released.
- National Public Health Surveillance System mandatory notification form will be filled out, the institution where the volunteer works will be informed, and the completed form will be sent.

- The volunteer will be informed that telephone follow-up will be carried out every 5 days until the symptoms are resolved or a maximum of six weeks after the diagnosis of COVID 19. In case of presenting any alarm sign during the follow-up, the patient will be recommended to attend the emergency department.

During the telephone follow-up, the volunteer's primary outcome (COVID 19 infection) will be classified as follows: asymptomatic, mild, moderate, or severe COVID. If the patient does not answer due to physical impossibility (e.g. intubation), communication with a companion or family member previously authorized by the patient will be sought.

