3.1. Study design

Randomized triple-blinded multicentric clinical trial, conducted in parallel, with two arms:

The trial will be performed with health care workers (Physicians, Nurses, Respiratory therapists, or nurse assistants) free of SARS-CoV-2 infection prior, recent or at the time of the inclusion and who directly care for confirmed or suspected cases of COVID-19 in the emergency room, general COVID wards or intensive care units. A screening at baseline will be carried out in order to evaluate for eligibility by performing: SARS-CoV-2 RT-PCR, SARS-CoV-2 IgG antibodies, as well as, hemogram, creatinine, serum phosphorus, AST, ALT, ELISA for HIV, surface Hepatitis B antigen antibodies, qualitative pregnancy test (b-HCG). Once

eligibility is verified participants will be randomly assigned to either an intervention or a control group.

The interventions consists in the administration of Tenofovir/ Emtricitabine (300 mg / 200 mg daily during 60 days) + Personal Protective Equipment (PPE) and the control consists in the administration of placebo (1 tablet daily during 60 days) + Personal Protective Equipment (PPE)

All participants will have PPE recommended for the preventions of COVID-19 by the WHO which include mayo dress, nonfluid long sleeve gown, ocular protection with goggles, face shield or visor and surgical mask in procedures that do not aerosolize. N-95 respirators are required for procedure that generate aerosols. For detailed description see Table 2.

The re-use of N-95 respirators will be allowed according to CDC and WHO guidelines. This taking into consideration the shortage of supplies for the actual situation. The N-95 continuous use will be for 8 hours and the N-95 intermittent use will be allowed up to 5 times with the precaution of storage in a paper and plastic bag label them with the participant name and placed them in a plastic recipient at the end of shifts(48).

After baseline evaluation and confirming eligibility an initial visit and 4 follow up visits at day 20, 40, 60, 75 days will be carried out. See Table 1 and Graph 1.

In the case of presenting COVID-19 related symptoms at any time after enrolling a SARS-CoV2 RT-PCR will be performed between day 1 to 5 of the onset of symptoms and will be repeated it after 72 hours in case that the first one is negative. In the case of having any positive SARS-CoV2 RT-PCR or SARS-CoV2 IgG SARS-CoV2 infection will be confirmed and the intervention will be suspended.

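### Masking is released for every infected participant before severity is classified, which contradicts the stated blinding

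*Combined protocol and SAP*

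**What the plan says.** Section 3.6.9, on what happens when a participant reaches the primary outcome, is triggered by any positive RT-PCR or IgG after the start of the study. One of its steps reads: "The volunteer will be instructed to suspend the intervention product, and the masking will be released". Telephone calls follow every 5 days until symptoms resolve, for at most six weeks after diagnosis. The infection is graded as asymptomatic, mild, moderate or severe during those calls.

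Other sections describe the masking differently:

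- Section 3.1 gives the design as "Randomized triple-blinded multicentric clinical trial, conducted in parallel, with two arms". For the same trigger it says only that "infection will be confirmed and the intervention will be suspended"; release of masking is not mentioned.
- Section 3.6.6 undertakes that investigators and volunteers stay blind while the study runs. Of volunteers it says "they will not be informed which intervention they are receiving". It continues "The researcher will be blind throughout the" volunteer's follow-up, and "only the central pharmaceutical chemist will know the assignment". Of the analyst's two-group code it says "This coding will only be revealed when the analysis is complete". It states no exception.
- Section 3.6.4 says of the bottles: "The only one who will know the information on the specific contents of the vials is the central pharmaceutical chemist of the study".

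Severity is a secondary outcome (Section 3.3). It is to be described and compared between groups (Section 2.2) and is analysed descriptively (Section 4).

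**The concern.** The release is routine. It follows from reaching the endpoint and does not depend on clinical need. It also comes at the contact where the result is given, before the calls in which severity is graded. Severity would therefore be reported from a trial described as triple-blinded, although masking had been lifted for every person being graded.

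The documents do not say who receives the allocation, or whether the person grading severity learns it. No separate masked assessor is named. A participant or caller who knows the allocation may report or record mild symptoms differently, and the asymptomatic and mild categories are separated by symptoms.

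A further point is inference only. If the released allocations reach the study database, the analyst's two-group code could be worked out before the analysis is complete.

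**Working it through.** **1. Does the release cover every primary-outcome case?** Section 3.3 defines the outcome as a positive RT-PCR or a positive IgG in any follow-up specimen, with asymptomatic participants included under RT-PCR. Section 3.6.9 has the same trigger and no further condition. It does.

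**2. Does it precede grading of severity?** Release belongs to the contact made on the positive result. Grading takes place during the later telephone follow-up. It does.

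**3. Can the release be reconciled with Section 3.6.6 by choosing the recipient?**

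| Recipient | Statement it conflicts with |
|---|---|
| Volunteer | Volunteers are not told their intervention (3.6.6) |
| Researcher | Blind throughout the volunteer's follow-up (3.6.6) |
| Analyst | Code revealed only after the analysis (3.6.6) |
| Anyone but the central chemist | Only that person knows the assignment (3.6.6; bottle contents, 3.6.4) |

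The central chemist already holds the allocations, so release to that person would change nothing.

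**4. Does stopping the product require the allocation?** No. The product is suspended in both arms alike.

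**5. How many participants?** The counts use the planned sample size, so that was reproduced first. Inputs from Section 3.4 are risks of 0.10 and 0.05, alpha 0.05 (taken as two-sided), power 0.80 and 1:1 allocation.

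- Unpooled formula: (1.96 + 0.84)² × (0.10×0.90 + 0.05×0.95) / 0.05² gives 431.7, so 432 per arm and 864 in total.
- Pooled-variance formula: 435 per arm, 870 in total. The plan's 858 is within 2% of both.
- Losses of 10%: 858/0.90 = 953 and 858×1.10 = 944. The plan's 950 lies between them.

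Expected releases with 475 per arm:

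- Placebo: 475 × 0.10 = 47.5
- Active: 475 × 0.05 = 23.75
- Total: 71.25, and 71.25/950 = 7.5%

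Sensitivity of that count:

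- With 429 per arm: 42.9 + 21.45 = 64.
- With the sites' two-month incidence (3.3% to 13.7%, Section 3.4) as the control risk, and the assumed halving: 475 × 0.033 × 1.5 = 24 up to 475 × 0.137 × 1.5 = 98. At the 11.2% mean it is 80.

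**6. Which gradings are exposed?** Moderate and severe rest on hospital or ICU care (Section 3.3). Symptom-triggered cases have reported two or more symptoms before testing (Section 3.6). That leaves mainly the asymptomatic/mild boundary in cases found by scheduled testing. As an illustration, assume that 18% to 46.5% are asymptomatic, the range Section 1.3 gives for screening in confined populations:

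- Placebo: 47.5 × 0.18 = 8.6 to 47.5 × 0.465 = 22.1
- Active: 23.75 × 0.18 = 4.3 to 23.75 × 0.465 = 11.0
- Total: about 13 to 33

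Moving one case across the boundary changes an arm's proportion by 1/47.5 = 2.1 points (placebo) or 1/23.75 = 4.2 points (active).

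**The case against.** The strongest reply is that Section 4 lets follow-up run until the primary outcome. Blinding throughout follow-up would then end when masking is released, and the chemist-only clause, which explains how that blinding is kept, might end with it. This reading is arguable but does not settle the matter. The definition belongs to the primary time-to-event analysis, and Section 3.6.9 itself continues with telephone follow-up. Section 3.6.6 also promises blinding of investigators and volunteers while the study runs, without that limit.

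Some narrower points stand. Section 3.1 supplies only the triple-blinded label and a suspension-only rule, so the direct conflict is with Section 3.6.6. Section 3.6.4 deals mainly with concealment before treatment starts and adds little weight.

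Harm is also not demonstrated. Severity is secondary and descriptive. The scheduled visits at days 40, 60 and 75 include a clinical evaluation, and Appendix 3 records symptoms and their start date, the date of a positive RT-PCR and admission dates. Symptoms up to the detecting visit can therefore be recorded before release, and part of the grading can be checked. The 13 to 33 cases are not a count of gradings that would change, and Section 3.6 itself puts test sensitivity in asymptomatic infection at only about 30% to 40%.

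Finally, the SOPs and investigator's manual are not in the file and may name the recipient and timing. They would not remove a contradiction within the protocol. Appendix 3 lists no variable for the release itself.

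**Conclusion.** The concern holds. Section 3.6.9 releases masking for every primary-outcome case, before severity is graded, and this cannot be squared with Section 3.6.6. At the planned risks and 475 per arm it affects about 71 of 950 participants, or about 24 to 98 across the sites' observed incidence with the assumed halving. Those are all the participants whose severity is to be compared.

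The consequence is limited. The gradings open to influence are mainly those between asymptomatic and mild; the 13 to 33 cases shown for that boundary depend on an assumed asymptomatic share. The documents give neither the direction nor the size of any bias. The unmasked person's infection endpoint is already fixed by a laboratory result. The sponsor should correct this, because a stated safeguard is withdrawn for a planned between-arm comparison, but it does not undermine the primary analysis.

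**What to change.** Reconcile Sections 3.6.6 and 3.6.9 by deleting the clause on release of masking and leaving suspension of the product as written. Allocation then stays concealed from the participant and from the person classifying severity, and from the analyst until the analysis is complete, as Section 3.6.6 already provides.

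Any individual unmasking for clinical need should go through the holder of the allocations, the central pharmaceutical chemist in Sections 3.6.4 and 3.6.6. It should be kept out of the analysis database and logged with date, reason and recipient. The criteria for such unmasking are for the sponsor and are not proposed here.

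If the sponsor has a reason to keep the release, Section 3.6.6 should state the exception, who learns the allocation and when. The person classifying severity should then be kept unaware; otherwise severity should be reported as an unmasked outcome.

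The cost is a change of protocol wording and an unmasking log. Infected participants would learn their allocation later. The consent text is not in the file, so the sponsor should check that it does not promise earlier disclosure.
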